10.4 Vital signs, physical findings, and other observations related to safety

10.4.1 Vital signs

The following vital signs measurements will be obtained:

- Pulse rate
- Systolic and diastolic blood pressure
- Body weight
- Temperature (oral preferred, ear or axillary permitted)

A by-study participant listing of all vital sign measurements and change from Baseline will be presented by treatment group and timepoint. The listing will include a flag for measurements identified as markedly abnormal MA as calculated by the criteria outlined in Section [13.2 Error! Reference source not found.](#)

Descriptive statistics will be reported for all vital sign measurements. Measured values and changes from Baseline will be summarized by vital signs variables, timepoint and treatment group.

Summarization will be as treated, study participants who missed treatments will not be summarized. Repeated and unscheduled measurements will be handled as described in Section [4.2.8](#).

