14.1.2 Safety Set

The Safety Set (SS) will consist of all enrolled study participants who were administered at least 1 dose of rozanolixizumab.

Safety variables will be analyzed using the SS.

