14.3 Planned safety analyses

14.3.1 Safety analyses

The incidence of study participants with TEAEs will be determined. Furthermore, the absolute and relative frequencies for study participants with a given TEAE with respect to the preferred term according to the latest available version of the Medical Dictionary for Regulatory Activities

(MedDRA®), will be determined within each system organ class. Additional tables will summarize TEAEs by maximum severity and causal relationship with rozanolixizumab, as judged by the investigator. Adverse events will be categorized by severity according to the National Institutes for Health CTCAE version 5.0 grading (National Institutes for Health, 2017). In case the CTCAE grading is not available, the intensity (mild/moderate/severe) will be utilized. The TEAEs leading to discontinuation of IMP and the serious TEAEs will also be summarized. The action taken, time of onset relative to dosing, actual dose received, and duration of each AE will be listed only.

For the continuous laboratory variables, the values and changes from Baseline will be descriptively summarized at each time point. For categorized values according to the reference range, shift tables from Baseline to each post-Baseline time point will be presented for selected variables to be defined in the SAP. Values outside the reference range will be flagged in the data listings.

Descriptive statistics will be presented for ECG value and changes from Baseline over time based on the mean of the triplicate assessments at each time point. Categorical analyses for QTc, eg, QTc increase >60msec, will also be performed.

Descriptive statistics will be reported for all vital sign measurements (including BP, PR, temperature, and body weight). Measured values and changes from Baseline will be summarized by time point.

Physical and neurological examination findings and the results of any pregnancy testing will be presented in listings only. Results will be listed for any study participants who complete a headache questionnaire, undergo stool sampling, or lumbar puncture, etc.

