1 INTRODUCTION

The purpose of this statistical analysis plan (SAP) is to provide all information necessary to perform the required statistical analyses of study CIDP04. It defines the summary tables, figures, and listings (TFLs) to be included in the Clinical Study Report (CSR).

This SAP is based upon, and assumes familiarity, with the following documents:

- Final Protocol: 14 Dec 2018
- Protocol Amendment 2: 12 Jul 2019
- Protocol Amendment 3: 16 Mar 2020

Unless otherwise specified below, the study will be analyzed as described in the most recent version of the protocol (European Union Drug Regulating Authorities Clinical Trials [EudraCT]-Number: 2018-004392-12).

If a future protocol amendment necessitates a substantial change to the statistical analysis of the study data, this SAP may be amended accordingly. Changes to the analysis from the protocol are documented in section 3.9.

The content of this SAP is compatible with the International Council for Harmonisation (ICH)/Food and Drug Administration (FDA) E9 Guidance documents.

UCB is the Sponsor and PAREXEL is the Contract Research Organization (CRO) for this study.

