3.5.2 Safety Set

The Safety Set (SS) will consist of all enrolled study participants who were administered at least one dose of rozanolixizumab in CIDP04.

All safety variables will be analyzed using the SS.

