4.3 Handling of measurements obtained at the premature end of treatment visit

Study participants who withdraw from the study prematurely will be encouraged to return for the PEOT visit. The following rules will apply with regard to the inclusion of the results obtained at the PEOT in the descriptive summaries:

- Any measurements (safety, immunological and PD assessments) conducted at the PEOT should be included in the summaries for the respective scheduled visit, if the PEOT occurs at the time of the next scheduled visit (within the tolerance window specified in the protocol);
- If the PEOT does not correspond to the day of a scheduled visit, the safety and other relevant assessments of the PEOT should be mapped to the nearest scheduled visit, relative to the Baseline visit date, following the last scheduled visit where assessments are available;
- If the date of the PEOT is equidistant between 2 scheduled visits at which no scheduled assessments were performed, the assessments from the PEOT will be mapped to the earliest of these visits.

Different domains from the same PEOT may be re-assigned to different study visits depending on the study schedule of assessments, ie, measurements obtained at the PEOT can only be mapped to a scheduled visit at which the respective assessment was intended to be measured. Assessments from the PEOT that are mapped to scheduled visits will be flagged in the data listings.

Visits after the PEOT following the schedule of the 8-Weeks Observation period, will be mapped to the corresponding planned visit. Assessments on these visits will be flagged in the data listing.

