10 SAFETY ANALYSES

All safety analyses will be presented using the SS. Listings will be presented by treatment group and study participant; tabulations will be presented by treatment group and visit/timepoint (if applicable).

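### SAP 10.4.1 and 10.4.2 leave participants with missed doses out of the vital-sign and ECG summaries, against the Safety Set rule; the exclusion is neither defined nor recorded in SAP 3.9

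*SAP*

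**What the plan says.** SAP 3.5.2 defines the Safety Set as enrolled participants "who were administered at least one dose of rozanolixizumab in CIDP04" and adds "All safety variables will be analyzed using the SS". The opening of SAP section 10 repeats this: "All safety analyses will be presented using the SS". Protocol 14.1.2 says the same: "Safety variables will be analyzed using the SS". None of these makes membership depend on later doses.

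For vital signs, protocol 14.3.1 says "Measured values and changes from Baseline will be summarized by time point". It plans the ECG summaries over time from the mean of the triplicates. Neither plan excludes anyone for missed doses. Protocol 4.1.2 and SAP 2.2.1.2 define both variables at each scheduled assessment in the Treatment and Observation Periods.

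SAP 10.4.1 and 10.4.2 then each contain the sentence "Summarization will be as treated, study participants who missed treatments will not be summarized".

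On departures from the protocol, SAP section 1 says "Changes to the analysis from the protocol are documented in section 3.9". The exclusion does not appear there.

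**The concern.** The sentence cannot refer to people who were never dosed, because they are already outside the Safety Set. It must therefore remove Safety Set members, or some of their data, from the summaries. It gives no number of misses, no period, and no unit of exclusion (visit or participant). Two programmers could build different by-visit tables from the same data, including the QTcF category counts.

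Missed doses are also not purely logistical. Protocol 6.4.1.3 requires a temporary hold when total IgG is below 1 g/L, and 6.4.1.2 allows one for a persisting or recurrent non-serious infection with IgG from 1 to below 2 g/L. The excluded participants may therefore not be a random subset. The study's primary objective is long-term safety, and these tables are the only aggregate vital-sign and ECG outputs that 10.4.1 and 10.4.2 describe.

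**Working it through.** **1. Is the exclusion defined anywhere?** The SAP's only missed-dose threshold is in 3.5.4: more than two missed administrations within three months. It defines the MFAS, an efficacy set, and 10.4 does not refer to it. SAP 3.6 uses the treatment actually received only to allocate participants to a treatment group, so the words about summarising as treated do not explain leaving people out.

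**2. Does it fit the neighbouring text?**
- SAP 10.4.1 also promises descriptive statistics for all vital-sign measurements.
- SAP 10.4.2 bases QTcF percentages on participants with a non-missing value at the time point. That does not fit an exclusion of people who have values.
- SAP 10.3 has no such rule, so the same participant at the same visit could be in the laboratory tables but absent from the ECG and vital-sign tables.
- SAP 4.3, for a premature end-of-treatment visit that coincides with the next scheduled visit, says "Any measurements (safety, immunological and PD assessments) conducted at the PEOT should be included in the summaries for the respective scheduled visit"; other such visits are mapped to the nearest scheduled visit. No dose is planned there. Whether these participants count as having missed treatments is not said.

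**3. Can values exist at undosed visits?** Yes. Protocol 8.3.2 schedules vital signs at Part 2 home visits and allows IMP to be withheld at them. How often this will happen is not stated.

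**4. How far apart are the readings of the sentence?** The documents give no figure to reproduce, so this counts planned assessments at dosing visits only, leaving out the Observation Period.

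Vital signs (protocol 9.3.2):
- Visits 2 to 4: 3 × 4 = 12
- Visits 5 to 25: 21 × 3 = 63
- Part 1: 12 + 63 = 75
- Part 2, Weeks 25 to 76: 52 × 2 = 104
- Both parts: 75 + 104 = 179

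ECG visits (protocol Table 5-1, 8.2.10 and 8.3.1):
- Part 1: Visits 2, 3, 4, 5, 8, 10, 12, 14, 16, 18, 20, 22 and 24 = 13
- Part 2: Weeks 25, 37, 49 and 61 = 4
- Both parts: 17

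For a participant with exactly one missed dose, a visit-level reading loses at most what was recorded at that visit. A participant-level reading also discards everything from the visits where the dose was given:

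| Participation | Missed dose at | Vital-sign readings at dosed visits | ECGs at dosed visits |
|---|---|---|---|
| Part 1 only (24 doses) | Visit 3 or 4 | 75 − 4 = 71 of 75 | 12 of 13 |
| Part 1 only | Visits 5 to 25 | 75 − 3 = 72 of 75 | 12 or 13 of 13 |
| Both parts (24 + 52 = 76 doses) | Visit 3 or 4 | 179 − 4 = 175 of 179 | 16 of 17 |
| Both parts | Visits 5 to 25 | 179 − 3 = 176 of 179 | 16 or 17 of 17 |
| Both parts | Part 2 | 179 − 2 = 177 of 179 | 16 or 17 of 17 |

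**5. Does the threshold matter?** As an illustration only, assume each dose is missed independently with probability p. The share of participants with at least one miss in n doses is 1 − (1 − p)^n. The share with at least two is 1 − (1 − p)^n − np(1 − p)^(n−1).

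| Assumed p | ≥1 miss, n = 24 | ≥1 miss, n = 76 | ≥2 misses, n = 24 | ≥2 misses, n = 76 |
|---|---|---|---|---|
| 0.5% | 11% | 32% | 1% | 6% |
| 1% | 21% | 53% | 2% | 18% |
| 2% | 38% | 78% | 8% | 45% |
| 5% | 71% | 98% | 34% | 90% |

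These are not predictions: p is assumed, and IgG-related holds would cluster within participants. The table shows only that the choice between one miss and two changes who is summarised.

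**The case against.** The best defence is that the sentence is a by-visit handling rule: the tables are by time point, so only values from a visit without a dose are dropped and Safety Set membership is unaffected. Vital signs are timed around the infusion, so without one there is no end-of-infusion reading to summarise. Protocol section 14 leaves detail to the SAP, and other display rules, such as the 33% limit in SAP 4.2.2, are not listed in 3.9 either. The listings with marked-abnormality flags keep every value, the TEAE tables are unaffected, and no test or decision depends on these tables.

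Part of this stands. The visit-level reading is possible and loses little, the participant-level counts show one reading rather than an expected loss, and the consequence is limited. But the sentence speaks of participants, not visits. Even at visit level it drops scheduled safety values of Safety Set members. Infusion timing does not explain the ECG sentence or the loss of a predose reading. The lines on all measurements and on the non-missing QTcF denominator add to the contradiction rather than resolve it. As for 3.9, it does list a comparable exclusion, that of efficacy assessments after rescue medication, so this one belongs there too.

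The premature end-of-treatment mapping in SAP 4.3 is weak evidence of conflict. So is the rule in SAP 2.3 on making up assessments after a missed site visit, which concerns conduct rather than tabulation. The conclusion needs neither.

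**Conclusion.** The concern holds. As written, the sentence removes on-study safety data of Safety Set members from the vital-sign and ECG summaries, against SAP 3.5.2, SAP section 10 and protocol 14.1.2. The exclusion is undefined and undeclared.

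The overall size cannot be stated without a missed-dose rate. For a participant with one missed dose, the discrepancy between readings ranges from what was recorded at one visit to nearly all of that participant's planned values. Participants on hold for low IgG or infection may be under-represented. No document links such holds to ECG or blood-pressure values, so no direction of bias can be claimed. The point should be fixed, but it is confined to descriptive tables.

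**What to change.** Delete the sentence from SAP 10.4.1 and 10.4.2. Summarise every Safety Set participant who has a value at the time point and show n for each. If an on-dose summary is also wanted, make it supplementary, define a missed treatment visit by visit, and record it in SAP 3.9.

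The cost is SAP wording only, before two sets of tables are programmed. No further data are needed.

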10.4.2 Electrocardiograms

Standard 12-lead ECG recordings will be taken in triplicate with the study participant resting in the supine position for at least 15 minutes and before obtaining any blood samples for assessments of laboratory variables. The following variables will be reported:

- Heart rate
- RR interval
- PQ/PR interval
- QRS duration
- QT interval

- QT corrected for heart rate using Fridericia's formula ($QTcF = QT / \sqrt[3]{RR}$)

The individual measurements and the mean of the triplicate measurements will be reported in the by-study participant listings. The listing will also include the change from Baseline (based on the mean of the triplicate measurements at each timepoint) and will be presented by treatment group and by timepoint. The listing will also include a flag for values identified as MA as defined by the criteria outlined in [Section 13.2](#)**Error! Reference source not found.**

Summarization will be as treated, study participants who missed treatments will not be summarized.

Measured values and changes from Baseline will be summarized by treatment group at each timepoint and by ECG variable (based on the mean of the triplicate values at each timepoint).

The following cut-points in QTcF (raw data and change from Baseline) will be summarized categorically by treatment group (number and percentage of participants) and visit/timepoint. The denominator for the percentages will be the number of participants with a non-missing measurement for the variable at the specific visit/timepoint.

Raw QTcF data:

- <450msec
- ≥450msec to <480msec
- ≥480msec to <500msec
- ≥500msec

Change from Baseline QTcF:

- <30msec
- ≥30ms to <60msec
- ≥60msec

Electrocardiogram findings for the individual triplicate measurements will be listed separately.

Repeated and unscheduled measurements will be handled as described in [Section 4.2.8](#).

In the event that the complete set of triplicate measurements is not available at a specified timepoint the data will be handled as described in [Section 4.2.6](#).

10.4.3 Suicidality

A full Columbia Suicide Severity Rating Scale (C-SSRS) assessment will be performed only when study participant has a positive response to the suicidal ideation query. Results of suicidal ideation and C-SSRS will be listed by treatment group, study participant and time point.

10.4.4 Other safety variables

Results of Serum and Urine pregnancy test will be listed.

Results of tuberculosis signs and symptoms questionnaire will be listed.

Results of interferon-gamma release assay (IGRA) tuberculosis test will be listed.

Physical and neurological examination findings will be listed.

Results of serology testing for human immunodeficiency virus (HIV), Hepatitis B and Hepatitis C will be listed.

Study participants experiencing severe headache will complete the Headache Questionnaire daily until resolution (ie, if headache becomes moderate or mild, normal collection of AEs should apply). The results of the headache questionnaire will be listed for each study participant.

At the clinic visit when the severe headache is reported, the Headache Questionnaire will be followed by a neurological assessment (including fundoscopy). If the severe headache is initially reported at a home visit or during a telephone call, the participant should be reviewed at the study site as soon as is practically possible for further investigations. Further workup will be performed at the discretion of the investigator and may include, eg, a computed tomography scan, magnetic resonance imaging and/or a lumbar puncture for cerebral spinal fluid collection. In addition, samples for exploratory biomarkers should be taken for participants experiencing severe headache (Table 5-2 of the protocol). These investigations will be performed to further understand the mechanism of headache in these participants.

The results of the headache questionnaire, neurological examination and any additional tests performed (CT scan, fundoscopy and LP for CSF collection) will be listed for each participant having experienced severe headache. No summary tabulations will be provided for these assessments

Stool collection and analysis will be performed for participants reporting moderate or severe diarrhea. Results of the analysis will be listed for each participant. No summary tabulation will be provided for this assessment.

11 OTHER ANALYSES

Exploratory pharmacogenetics variables samples date/timepoint collection will be listed.

Exploratory proteins, and metabolites variables samples date collection will be listed.

13 APPENDICES

13.1 Conversion of iRODS scores

Table 13-1: Nomogram

R-ODS summed raw score	Rasch person location (logits)	centile metric	Corresponding SE $SE = 0.4248 - 0.0016 * \text{location} + 0.0140 * \text{location}^2$
0	-6.95	0	1.11
1	-6.03	6	0.94
2	-5.36	11	0.84
3	-4.87	14	0.76
4	-4.48	16	0.71
5	-4.14	19	0.67
6	-3.84	21	0.64
7	-3.57	22	0.61
8	-3.32	24	0.58
9	-3.09	26	0.56
10	-2.87	27	0.54
11	-2.66	28	0.53
12	-2.46	30	0.51
13	-2.26	31	0.5
14	-2.07	32	0.49
15	-1.88	34	0.48
e	-1.70	35	0.47
17	-1.52	36	0.46
18	-1.33	37	0.45
19	-1.15	39	0.45
20	-0.97	40	0.44
21	-0.79	41	0.43
22	-0.61	42	0.43
23	-0.42	43	0.43
24	-0.24	45	0.43
25	-0.05	46	0.42
26	0.14	47	0.42
27	0.34	48	0.43
28	0.53	50	0.43
29	0.73	51	0.43
30	0.94	52	0.44
31	1.15	54	0.44

Table 13–1: Nomogram

R-ODS summed raw score	Rasch person location (logits)	centile metric	Corresponding SE SE= $0.4248 - 0.0016 \times \text{location} + 0.0140 \times \text{location}^2$
32	1.36	55	0.45
33	1.58	57	0.46
34	1.81	58	0.47
35	2.04	60	0.48
36	2.28	61	0.49
37	2.54	63	0.51
38	2.80	65	0.53
39	3.09	67	0.55
40	3.40	69	0.58
41	3.74	71	0.61
42	4.11	73	0.65
43	4.54	76	0.71
44	5.03	80	0.77
45	5.59	83	0.85
46	6.25	88	0.96
47	7.07	93	1.11
48	8.11	100	1.33

13.2 MA criteria for Rozanolixizumab program

The following criteria will be applied in the determination of marked abnormalities for laboratory assessment values. They are based on Version 5 of the Common Terminology Criteria for Adverse Events (CTCAE) grade 3 or higher criteria unless otherwise noted.

Table 13-2: MA Values for Rozanolixizumab Clinical Development Program Based on CTCAE Grades

Domain	Parameter	Unit (conventional)	Unit (standard)	Marked Abnormality criteria
Chemistry	AST (SGOT)	U/L	U/L	>5.0 x ULN
Chemistry	ALT (SGPT)	U/L	U/L	>5.0 x ULN
Chemistry	ALP (Alkaline Phosphatase)	U/L	U/L	>5.0 x ULN

Table 13-2: MA Values for Rozanolixizumab Clinical Development Program Based on CTCAE Grades

Domain	Parameter	Unit (conventional)	Unit (standard)	Marked Abnormality criteria
Chemistry	GGT (Gamma Glutamyl Transferase)	U/L	U/L	>5.0 x ULN
Chemistry	Bilirubin (Total)	mg/dL	umol/L	>3.0 x ULN if Baseline value is normal; >3.0 x Baseline value if Baseline is abnormal
Chemistry	Albumin	g/dL	g/L	<2 g/dL; <20 g/L
Chemistry	Creatinine	mg/dL	umol/L	>3.0 x ULN
Chemistry	Estimate glomerular filtrate rate (eGFR) ¹	mL/min/1.73 m ²	mL/min/1.73 m ²	eGFR <29 mL/min/1.73 m ²
Chemistry	C reactive protein (CRP) ²	mg/L	mg/L	>10 mg/L
Chemistry	Calcium	mg/dL	mmol/L	Low: Corrected serum calcium of <6.0 mg/dL; <1.5 mmol/L
Chemistry				High: Corrected serum calcium of >12.5 mg/dL; >3.1 mmol/L
Chemistry	IgG	g/L	g/L	≤ 1 g/L
Chemistry	Potassium	mmol/L	mmol/L	Low: <2.5 mmol/L High: >6.0 mmol/L
Chemistry	Sodium	mmol/L	mmol/L	Low: <125 mmol/L High: >155 mmol/L
Chemistry	Glucose	mg/dL	mmol/L	Low: <40 mg/dL; <2.2 mmol/L High: > 250 mg/dL; >13.9 mmol/L
Chemistry	Total Cholesterol	mg/dL	mmol/L	>400 /dl; >10.34 mmol/L
Chemistry	Triglycerides	mg/dL	mmol/L	>500 mg/dl; >5.7 mmol/L
Hematology	Hemoglobin	g/dL	g/L	<8.0 g/dL; <80 g/L
Hematology	WBC (Leukocytes) ⁴	10 ⁹ /L	10 ⁹ /L	Low: <2.0 x 10 ⁹ /L High: >30 x 10 ⁹ /L
Hematology	Lymphocytes Absolute	10 ⁹ /L	10 ⁹ /L	Low: <0.5 x 10 ⁹ /L High: >20 x 10 ⁹ /L
Hematology	Neutrophils Absolute	10 ⁹ /L	10 ⁹ /L	<1.0 x 10 ⁹ /L

Table 13-2: MA Values for Rozanolixizumab Clinical Development Program Based on CTCAE Grades

Domain	Parameter	Unit (conventional)	Unit (standard)	Marked Abnormality criteria
Hematology	Platelets	$10^9/L$	$10^9/L$	$<50.0 \times 10^9/L$
Vital Signs	Pulse Rate	bpm	bpm	≤ 50 and a decrease from Baseline of ≥ 15 ≥ 120 and an increase from Baseline of ≥ 15
Vital Signs	Systolic Blood Pressure	mmHg	mmHg	≤ 90 and a decrease from Baseline of ≥ 20 ≥ 180 and an increase from Baseline of ≥ 20
Vital Signs	Diastolic Blood Pressure	mmHg	mmHg	≤ 50 and a decrease from Baseline of ≥ 15 ≥ 105 and an increase from Baseline of ≥ 15
Vital Signs	Temperature	°F	°C	>101 °F (38.3 °C)
Vital Signs	Body Weight			$\geq 10\%$ decrease from Baseline $\geq 10\%$ increase from Baseline
ECG	QT interval	ms	ms	≥ 500 ms
				≥ 60 ms increase from Baseline
ECG	QTc(F)	ms	ms	≥ 500 ms
				≥ 60 ms increase from Baseline
ECG	PR interval	ms	ms	Treatment-emergent value >200 ms
ECG	QRS interval	ms	ms	Treatment-emergent value >100 ms
ECG	Heart rate	bpm	bpm	<50 bpm
				>120 bpm

Abbreviations: ALT = alanine aminotransferase; AST = aspartate aminotransferase; dL = deciliter; GGT: gamma-glutamyltransferase; L = liter; mg = milligram; mmol = millimoles; μ g = microgram; U = unit; ULN = upper limit of normal

Note: Marked abnormality criteria are defined by Grade 3 or higher events according to the Common Terminology for Adverse Events (CTCAE), Version 5.0, November 17, 2017 unless otherwise noted.

¹eGFR is calculated using the Chronic Kidney Disease Epidemiology Collaboration or CKD-EPI formula (https://qxmd.com/calculate/calculator_251/egfr-using-ckd-epi) which is $eGFR = 141 * \min(\text{Scr}/\kappa, 1)^\alpha * \max(\text{Scr}/\kappa, 1)^{-1.209} * 0.993^{\Delta\text{ge}} * 1.018$ [if female] * 1.159 [if black]; where Scr is serum creatinine (mg/dL), κ is 0.7 for females and 0.9 for males, α is -0.329 for females and -0.411 for males, min indicates the minimum of Scr/ κ or 1, and max indicates the maximum of Scr/ κ or 1. For derivation from values in standard units (umol/L) the κ values are 61.9 for females and 79.6 for males.

²Includes CRP and High Sensitivity (HS) CRP. Reference for marked abnormality criteria: Nehring, S.M.; Goyal, A.; Patel, B.C. (2020). StatPearls Publishing, web link: <https://www.ncbi.nlm.nih.gov/books/NBK441843/>.

³Immunoglobulin G criterion based on immunodeficiency literature and noted in RLZ study protocols.

⁴WBC (Leukocytes) markedly abnormal high criterion is not based on Version 5 CTCAE Grade 3 or higher criteria. Due to the mechanism of action of RLZ, the safety alert is related to infection risk which would be identified by a

lower cut-point than the standard which is related to acute leukemias. A markedly abnormal high cut-point $>30 \times 10^9/L$ is applied to flag leukocytosis (George 2012).

